Appendix G: Ann Arbor Stage

Ann Arbor Stage

Stage I:

- I = Involvement of a single lymph node region.
- IE = Localized involvement of a single extralymphatic organ or site.

Stage II:

- II = Involvement of 2 or more lymph node regions on the same side of the diaphragm.
- IIE = Localized involvement of a single associated extralymphatic organ or site and its regional lymph nodes with or without other lymph node regions on the same side of the diaphragm.

Stage III:

- III = Involvement of lymph node regions on both sides of the diaphragm.
- IIIE = Involvement of lymph node regions on both sides of the diaphragm accompanied by localized involvement of an extralymphatic organ or site.
- IIIS = Involvement of lymph node regions on both sides of the diaphragm accompanied by involvement of the spleen*.
- IIIS+IIIE = Both IIIS+IIIE

Stage IV:

- IV = Disseminated (multifocal) involvement of 1 or more extralymphatic sites with or without associated lymph node involvement or isolated extralymphatic organ involvement with distant (non-regional) nodal involvement.
- IVE = Extranodal lymphoid malignancies arise in tissues separate from, but near, the major lymphatic aggregates.

Appendix H: ECOG Performance Status Criteria

The following table presents the ECOG performance status scale³²:

ECOG Performance Status Scale	
0	Normal activity. Fully active, able to carry on all pre-disease performance without restriction
1	Symptoms but ambulatory. Restricted in physically strenuous activity, but ambulatory and able to carry out work of a light or sedentary nature (eg, light housework, office work).
2	In bed <50% of the time. Ambulatory and capable of all self-care, but unable to carry out any work activities. Up and about more than 50% of waking hours.
3	In bed >50% of the time. Capable of only limited self-care, confined to bed or chair more than 50% of waking hours.
4	100% bedridden. Completely disabled. Cannot carry on any self-care. Totally confined to bed or chair.

Appendix I: Functional Assessment of Cancer Therapy for Lymphoma (FACTLym) (Version 4)

Below is a list of statements that other people with your illness have said are important. Please circle or mark one number per line to indicate your response as it applies to the past 7 days.

PHYSICAL WELL-BEING		Not at all	A little bit	Some- what	Quite a bit	Very much
GP1	I have a lack of energy	0	1	2	3	4
GP2	I have nausea	0	1	2	3	4
GP3	Because of my physical condition, I have trouble meeting the needs of my family	0	1	2	3	4
GP4	I have pain	0	1	2	3	4
GP5	I am bothered by side effects of treatment	0	1	2	3	4
GP6	I feel ill	0	1	2	3	4
GP7	I am forced to spend time in bed	0	1	2	3	4

SOCIAL/FAMILY WELL-BEING		Not at all	A little bit	Some- what	Quite a bit	Very much
GS1	I feel close to my friends	0	1	2	3	4
GS2	I get emotional support from my family	0	1	2	3	4
GS3	I get support from my friends	0	1	2	3	4
GS4	My family has accepted my illness	0	1	2	3	4
GS5	I am satisfied with family communication about my illness	0	1	2	3	4
GS6	I feel close to my partner (or the person who is my main support)	0	1	2	3	4
Q1	Regardless of your current level of sexual activity, please answer the following question. If you prefer not to answer it, please mark this box and go to the next section.					

GS7	I am satisfied with my sex life	0	1	2	3	4
-----	---------------------------------	---	---	---	---	---

Please circle or mark one number per line to indicate your response as it applies to the past 7 days.

EMOTIONAL WELL-BEING

		Not at all	A little bit	Some- what	Quite a bit	Very much
GE1	I feel sad	0	1	2	3	4
GE2	I am satisfied with how I am coping with my illness	0	1	2	3	4
GE3	I am losing hope in the fight against my illness	0	1	2	3	4
GE4	I feel nervous	0	1	2	3	4
GE5	I worry about dying	0	1	2	3	4
GE6	I worry that my condition will get worse	0	1	2	3	4

FUNCTIONAL WELL-BEING

		Not at all	A little bit	Some- what	Quite a bit	Very much
GF1	I am able to work (include work at home)	0	1	2	3	4
GF2	My work (include work at home) is fulfilling	0	1	2	3	4
GF3	I am able to enjoy life	0	1	2	3	4
GF4	I have accepted my illness	0	1	2	3	4
GF5	I am sleeping well	0	1	2	3	4
GF6	I am enjoying the things I usually do for fun	0	1	2	3	4
GF7	I am content with the quality of my life right now	0	1	2	3	4

Please circle or mark one number per line to indicate your response as it applies to the past 7 days.

ADDITIONAL CONCERNS		Not at all	A little bit	Some-what	Quite a bit	Very much
P2	I have certain parts of my body where I experience pain	0	1	2	3	4
LEU1	I am bothered by lumps or swelling in certain parts of my body (e.g., neck, armpits, or groin)	0	1	2	3	4
BRM3	I am bothered by fevers (episodes of high body temperature)	0	1	2	3	4
ES3	I have night sweats	0	1	2	3	4
LYM1	I am bothered by itching	0	1	2	3	4
LYM2	I have trouble sleeping at night	0	1	2	3	4
BMT6	I get tired easily	0	1	2	3	4
C2	I am losing weight	0	1	2	3	4
Ga1	I have a loss of appetite	0	1	2	3	4
HI8	I have trouble concentrating	0	1	2	3	4
N3	I worry about getting infections	0	1	2	3	4
LEU6	I worry that I might get new symptoms of my illness	0	1	2	3	4
LEU7	I feel isolated from others because of my illness or treatment	0	1	2	3	4
BRM9	I have emotional ups and downs	0	1	2	3	4
LEU4	Because of my illness, I have difficulty planning for the future	0	1	2	3	4

Appendix L: Patient Insurance

If required according to the national regulations for each participating country, the sponsor of the study will obtain insurance coverage for eventually occurring damage caused by the treatment or any actions taken according to the treatment plan. A certificate of insurance will be provided to the investigator in countries in which this document is required. The investigator, or an individual who is designated by the investigator, will inform the patient of the existence of the insurance, including the obligations arising from it. The study patients must be given access to the insurance documents and, on request, a copy of the general conditions of insurance.

DFS	Disease-free survival time
DR	Duration of Remission/Response
ECOG	Eastern Cooperative Oncology Group
ECG	Electrocardiogram
eCRF	electronic Case Report Form
EOT	End of Treatment
EWB	Emotional Well-being
FACT-G	Functional Assessment of Cancer Therapy – general
FACT-Lym	Functional Assessment of Cancer Therapy – lymphoma
FWB	Functional Well-being
Hb	Hemoglobin
HBV	Hepatitis-B-Virus
HCV	Hepatitis-C-Virus
HIV	Human immunodeficiency virus
ICF	Informed consent form
ICH	International Conference on Harmonisation
Ig	Immunoglobulin
ITT	Intention-To-Treat
LDH	Lactic DeHydrogenase
LLN	Lower limits of normal
LYMS	Lymphoma Subscale
MedDRA	Medical Dictionary for Regulatory Activities
MZL	Marginal Zone Lymphom
MRD	Minimal Residual Disease
NCI	National Cancer Institute
OS	Overall Survival
ORR	Overall response rate
PD	Progressive Disease
PFS	Progression Free Survival
Plt	Platelets
PWB	Physical Well-being
PR	Partial Remission
R	R Programming Language
SAE	Serious Adverse Event
SAP	Statistical Analysis Plan
SAS	Statistical Analysis System

SC	Subcutaneous
SD	Stable Disease
SOC	System Organ Class
SWB	Social/Family Well-being
TOI	Trial Outcome Index
TTF	Time to treatment failure
ULN	Upper Limit of Normal
WBC	White blood cells

1 Version History

Version 01, there are no other legacy versions.

2 Trial

2.1 Trial Summary and Trial Design

POLE-1 is a multicenter, single-arm, open-label, phase II trial of 18 cycles of Pembrolizumab and Rituximab in patients aged ≥ 18 years with previously untreated or relapsed MZL in need of treatment. The study comprises a treatment phase and the follow-Up phase. The study flow is as follows:

- Previously untreated or relapsed patients were screened for eligibility for the trial. If the patient was eligible for the study, the patient was registered before the first cycle of treatment.
- Patients who progressed at any time point during treatment were considered as treatment failure. They were followed up for overall survival until end of follow up period or death.
- Patients, who achieved at least a stable disease (SD) after treatment were followed up for response until progression/relapse and for overall survival until death.

The objective of this trial is to test the efficacy and toxicity of the treatment with Pembrolizumab/Rituximab in patients with MZL in need of treatment, who have failed or are not eligible for local therapy or relapsed after local or systemic therapy. For efficacy, the rate of complete remissions (according to the GELA criteria for gastric MALT or to the Cheson 2007 criteria for non-gastric extranodal, nodal and splenic MZL) after therapy will be primarily analysed. For toxicity assessment treatment associated adverse events, quality of life and cumulative incidence of secondary malignancies are documented.

Primary endpoint is the complete response (CR rate (CRR)) determined after end of treatment (18 cycles).

Secondary endpoints are the response rate (CR, PR, CR or PR), best response, time to best response, time to first response, progression free survival (PFS), time to treatment failure (TTF), duration of response (DR), cause specific survival (CSS), overall survival (OS), and quality of life during therapy.

Safety variables include AEs, SAEs, AESIs, laboratory parameters, and ECG. The severity of AEs will be graded using the NCI-CTCAE version 5.0 dictionary. An AE is defined as any event arising or worsening from the time a signed and dated informed consent form (ICF) is obtained until 110 days after the last study drug intake. Safety variables will be summarized by means of descriptive statistics and/or frequency tables as appropriate. All AEs, drug related AEs, serious AEs will be summarized by MedDRA classification (SOC and preferred term) and worst CTCAE grade.

[figure not shown]
The estimated duration of 12-18 months for patient recruitment on which the study design was based during initial planning has been exceeded substantially. The trial was stopped after inclusion of 22 (MALT lymphoma: n=8, splenic MZL: n=7, nodal MZL: n=7) of 56 planned patients since the initiation of the first site in Aug 2021. Additionally, eight patients not fulfilling the inclusion criteria had signed the ICF. The end of treatment visit of the last patient enrolled was 06 Dec 2024. Patients were included in Germany in 9 of 12 activated trial sites.

Further information about the trial is in the study protocol (V-3.0, 12 Apr 2021). Figure 1 shows the study design (see also CTP, page 33).

Fig.1: Study Design

POLE-1

Pembrolizumab in Marginal Zone Lymphoma

A multicenter open-label single-arm phase II study

Figure 1: POLE-1 study design. The Follow-Up phase follows after the treatment phase.

2.2 Biometrical Report

Results of statistical analysis (e.g. tables, figures, and summary statistics) will be provided to the Comprehensive Cancer Center / Department of Internal Medicine III / Institute of Experimental Cancer Research for preparation of the Synopsis according to the ICH E3 guideline (CPMP/ICH/137/95, July 1996). All outputs will be provided in English language (e.g. title of tables, listings or figures, names of variables in listings and tables). A separate biometrical report will not be provided.

3 Changes in the Conduct of the Study or Planned Analyses

The trial was stopped after recruiting of 22 of 56 planned patients because of delayed recruitment. Due to the small sample sizes, the exploratory use of univariate logistic regression analysis to investigate the influence of putative risk factors associated with CRR will not be done due to expected problems in model fitting. Likewise, the planned subgroup analyses for the MZL subtype strata MALT lymphoma, splenic MZL, nodal MZL will not be performed because summary statistics (e.g. mean, standard deviation, percentages) would be not meaningful. Instead, a simple description of the patients in the three subgroups will be provided (e.g. number of patients, time course, primary and secondary endpoints). No other deviations from the study protocol are known at time of finalizing this plan.

4 Analysis Sets

Core Analysis Population: As this study is a trial with only one treatment arm, all analyses will be performed only for one analysis population, the Core Analysis Population. This analysis population consists of all eligible patients included in the study who received at least one cycle of treatment. Patients without staging at regular end of treatment will be defined as non-responder (i.e. CR='NO'). Only patients who withdraw will be excluded from this analysis population (about 15% were expected). The results on efficacy in the Core Analysis Population were considered to be the main efficacy results (confirmatory results).

Safety Population: The safety population and the Core Analysis Population are identical in this trial.

5 Definitions

The following notation will be used in this SAP:

- the ***bold and italic marked word*** specify the data table in the SAS data base
- the *italic marked word* signs a variable or a value of a variable in the SAS data base

Primary endpoint:

Primary endpoint is the complete response (CR rate (CRR)) determined after end of treatment (18 cycles). Patients who progress before EOT will be treated as CR='NO' and will be included in the calculation of the primary endpoint. No primary endpoint will be determined for patients who withdraw. These patients will be excluded from the confirmatory data analysis but will be analysed in a separate exploratory sensitivity analysis of the primary endpoint.

Secondary Endpoints:

The following parameters are the secondary endpoints:

- Response rate
- Best response

- Time to best response
- Time to first response
- Progression free survival (PFS)
- Time to treatment failure (TTF)
- Duration of Response (DR)
- Cause specific survival (CSS)
- Overall survival (OS)
- Quality of life during trial (therapy)

For details of definition of each secondary endpoint, see part 7.5.

Safety variables:

Safety variables include AEs, SAEs, AESIs, laboratory parameters, and ECG. The severity of AEs will be graded using the NCI-CTCAE version 5.0 dictionary. An AE is defined as any event arising or worsening after start of study drug administration until 110 days (based on five times the terminal elimination half-life of Rituximab and Pembrolizumab) after the last study drug intake. Safety variables will be summarized by means of descriptive statistics and/or frequency tables as appropriate. All AEs, drug related AEs, serious AEs will be summarized by MedDRA classification (SOC and preferred term) and worst CTCAE grade.

Further variables:

Strata:

Data analysis according to the MZL subtype (strata MALT lymphoma, splenic MZL, and nodal MZL; variable *LYMTYPE* in table *TOL*) is limited due to the small patient numbers. A simple description will be performed instead.

6 Treatment of Data

Primary endpoint (complete response (CR rate (CRR) determined after end of treatment (18 cycles)): Patients who progress before EOT will be treated as CR='NO' and will be included in the calculation of the primary endpoint. Patients without staging at regular end of treatment will be defined as non-responder (i.e. CR='NO'). No primary endpoint will be determined for patients who withdraw. These patients will be excluded from the confirmatory data analysis but will be analysed in a separate exploratory sensitivity analysis of the primary endpoint.

Conversion of laboratory results: There is no standardized unit for the laboratory results (haematology, quantitative immunoglobulins, serum chemistry, thyroid hormones) in the data base (see annotated CRF at pages 105-113, 162f, 170-182, 186f). Therefore, the Comprehensive Cancer Center / Department of Internal Medicine III / Institute for Experimental Tumour Research will provide a table for the conversion of the laboratory results in units which will be used in the statistical analysis. These units are mentioned in the appendix (part 12.1). All conversion factors for units known at the time of finalization of this document are listed in the appendix (see part 12.1).

Harmonization of response categories for tumor assessment: For the statistical analysis of the primary endpoint and some secondary endpoints in the whole study population, a harmonization of the response categories for tumor assessment will be performed. This is due to the different response categories in the three subgroups (see annotated CRF at page 188ff, CTP at page 116ff). The response categories after the harmonization are complete remission (CR), partial remission (PR), stable disease (SD), progressive disease (PD) and not evaluated (NE). The appendix (part 12.2) shows the allocation of the single response categories.

Format of date variables: All date variables given in the database are strings in the format yyyy-mm-dd. In the statistical analysis, all date variables will be presented in the format dd/mm/yyyy.

General remarks: All data are stored in a data base provided by X-act Cologne Clinical Research GmbH. The data will be provided as SAS data (sas7bdat). No checks of plausibility and consistency will be carried out by the Institute of Epidemiology and Medical Biometry. All variables containing information for organisation, data entry, and data management are not mentioned in this document and will not be analysed. No English translation will be done in case of German data base entries.

7 Listing of Variables

The descriptive methods will be applied for whole study population. Additionally, a simple description will be performed for the MZL subtype strata MALT lymphoma, splenic MZL, nodal MZL instead subgroup analyses.

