10.1 Informed consent

All subjects must sign and date the most current IRB/IEC approved informed consent form. It is the responsibility of the investigator or a designated physician who is part of the study team to obtain informed consent in compliance with national requirements from each subject prior to any study related procedures or, where relevant, prior to evaluating the patient's suitability for the study.

The informed consent document used by the investigator for obtaining subject's informed consent must be reviewed and approved by the sponsor prior to IRB/IEC submission.

The investigator must explain to a potential patient the aims, methods, reasonable anticipated benefits and potential hazards of the trial and any discomfort it may entail. Patients will be

informed that they are free not to participate in the trial and that they may withdraw consent to participate at any time. They will be told which alternative treatments are available if they refuse to take part and that such refusal or withdrawal will not prejudice future treatment.

Confirmation that the informed consent form has been signed should occur before any study-specific procedures are performed and before patient registration. All subjects who receive protocol-specified therapy or specified treatment should be re-informed and should re-consent with at least every safety relevant updated version of the IRB/IEC approved informed consent form during study participation as applicable and per institutional guidelines.

Withdrawal in case the patients experiences an adverse event which indicates to the investigator that continued participation is not in the best interest of the patient is performed by the investigator. All data collected before the time point of withdrawal remain within the study database (according to AMG §40 (2a) 3) Consent will be sought from the patient, in order to be allowed to

- report further major outcome information (e.g. efficacy data)
- guarantee the safety of a patient
- comply with requirements to submit complete documents for authorisation

Documentation that informed consent occurred prior to the study subject's entry into the study and of the informed consent process should be recorded in the study subject's source documents including the date.

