12.6 Analysis Populations

12.6.1 Core Analysis Population

As this study is a trial with only one treatment arm, all analyses will be performed only for one analysis population, the Core Analysis Population. This analysis population consists of all eligible patients included in the study who received at least one cycle of treatment. Patients without staging at regular end of treatment will be defined as non-responder (i.e. CR='NO').

The results on efficacy in the Core Analysis Population were considered to be the main efficacy results (confirmatory results). Forty eight patients are planned to belong to the Core Analysis Population, see part 12.3 above.

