Details for f): Time to treatment failure is defined as the time of registration to discontinuation of therapy for any reason including death from any cause, progression, toxicity or add-on of new anti-cancer therapy. Time to treatment failure will be calculated as difference between time of registration (date of patient signed written informed consent; variable *RFICDAT* in table *DM*) and the earliest date of the event (discontinuation of therapy for any reason). The following information will be used for the determination of the last mentioned date:

- discontinuation of therapy for any reason: variable *EXENDATE_ET* in table *DSET* for *DSDECOD_ET* not in (1 3).
- death from any cause: the date of death will be determined using the variable *DTHDAT* in table *DSEOS*
- progression: the dates in table *RS* will be used as follows: nodal MZL and extragastric MALT lymphoma: variable *RSDAT_NMZEG* for *RSORRES_NMZEG* = 4, extranodal gastric MALT lymphoma: variable *RSDAT_EGM* for *RSORRES_EGM* in (4 5), splenic MZL: variable *RSDAT_SMZ* for *RSORRES_SMZ* = 4. Additionally for the date of progression, the variable *RSDAT_ET* (table *DSET* for *DSDECOD_ET* = 3) will be used for identifying patients with PD.
- end of treatment: variable *RSDAT_ET* for *DSDECOD_ET* = 3 in table *DSET*
- death: variable *DTHDAT* for *DSDECOD_EST* = 4 in table *DSEOS*
- add-on of new anti-cancer therapy: variable *PRSTDAT* in table *PR2* for the first event in a patient

Patients alive without treatment failure are censored at the latest tumor assessment date.

Details for g): Duration of Response will be calculated in patients with response to therapy (CR, PR) from diagnosis of response to the date of progression, relapse or death from any cause. It will be calculated as difference between date of diagnosis of response and the earliest event date (progression, relapse or death from any cause). The date of diagnosis of response will be determined as variable *ASS_DAT* from the variables *RSDAT_NMZEG* (nodal MZL and extragastric MALT lymphoma), *RSDAT_EGM* (extranodal gastric MALT lymphoma) and *RSDAT_SMZ* (splenic MZL) in table *RS* for the variable *ACTIVITY_ID* = 'EOT_ASS' and *ASS_RESULT* in (1 2) (see section 'Details for a') above).

For the determination of the earliest event date, the following information will be used:

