8.2.5 Sensitivity Analyses

Sensitivity analyses are planned for the stability investigation of the result of the confirmatory analysis of the primary endpoint. Patients who withdraw will be excluded from the confirmatory data analysis but will be analysed in a separate exploratory sensitivity analysis. Two distinct scenarios will be regarded to investigate the influence of withdrawals. In a first scenario is the primary endpoint in all withdrawals set to CR='no'. In the second scenario is the primary endpoint in all withdrawals set to CR='yes'.

Another sensitivity analysis is planned for patients with discrepancy between using the modified 2007 Cheson criteria and the data base entries regarding the evaluation of the primary endpoint. If there are such patients, two further scenarios for the primary endpoint will be investigated: In the first scenario the modified 2007 Cheson criteria will be applied, in the second scenario the data base entries as entered by the sites will be used.

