8.2.6 Safety Analysis

Generally, safety evaluations include: adverse events and clinical laboratory parameters (hematology, serum chemistry, serum immunoglobulin (IgG, IgM, IgA), CRP). The severity of adverse events will be assessed using National Cancer Institute Common Terminology Criteria for Adverse Events, Version 5.0.

Analysis of adverse events (AE), serious adverse events (SAE) and adverse events of special interest (AESI): AEs, SAEs and AESIs will be listed in tabular form. Listings will be provided for all AEs, SAEs, AESIs, and for AEs of grade ≥ 3 , SAEs of grade ≥ 3 , AESIs of grade ≥ 3 . Furthermore, the proportion (incl. 95% confidence interval) of patients with at least one AE / SAE / AESI will be calculated.

Analysis of concomitant medication: The time course of concomitant medication will be provided for each patient as listing of main variables (*SUBJECTID*, *CMSPID*, *CMTRT*, *CMINDC*,

CMDSTXT, *CMFREQ*, *CMROUTE*, *CMROUTEOTH*, *CMSTDAT*, *CMONGO*, and *CMENDAT* in table **CM**) of each medication ordered by number of medication (variable *CMSPID* in table **CM**). **Analysis of clinical laboratory parameter (hematology, serum chemistry, serum immunoglobulin (IgG, IgM, IgA), and CRP):** For each of the parameters of hematology (hemoglobin, hematocrit, platelets, erythrocytes, leukocytes, neutrophils, lymphocytes), serum chemistry (potassium, LDH, ALT, AST, GGT, alkaline phosphatase, uric acid, and CRP), and immunoglobulin (IgA, IgG, IgM) the time course will be analysed descriptively in a separate table with results from descriptive statistics. There will be a separate row for each point in time (see CTP pages 106-110). Furthermore, for each parameter of haematology and serum chemistry the frequency of clinical significant ratings and not clinically significant ratings will be provided.

Analysis of ECG findings: The frequencies for 'Examination performed?' (yes/no) and result (negative/positive) will be calculated for each point in time. In case of a clinically significant result, the time course of the results in the respective patient will be listed (variable *EGORRES* in table **EG**). Additionally, the respective database record in table **MH1** will be listed in this case.

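### The safety population is set equal to the Core Analysis Population, so dosed patients who withdraw fall outside the AE, SAE and AESI proportions; how many of the 22 this affects is not given and may be zero

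*SAP*

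**What the plan says.** Protocol 12.6.1 defines the Core Analysis Population: "This analysis population consists of all eligible patients included in the study who received at least one cycle of treatment". SAP section 4 repeats that definition, says that all analyses use this one population, and adds: "Only patients who withdraw will be excluded from this analysis population (about 15% were expected". The protocol synopsis carries the same exclusion. SAP 4 then states, as protocol 12.6.2 also does: "The safety population and the Core Analysis Population are identical in this trial".

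The main safety summary is in SAP 8.2.6: "the proportion (incl. 95% confidence interval) of patients with at least one AE / SAE / AESI will be calculated". No other denominator is named there. The same section also says: "Listings will be provided for all AEs, SAEs, AESIs". The only analysis that brings withdrawn patients back is in SAP 8.2.5, and its scope is efficacy: "Sensitivity analyses are planned for the stability investigation of the result of the confirmatory analysis of the primary endpoint".

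Neither document defines withdrawal for the purpose of the analysis set.

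**The concern.** Leaving out patients who have no primary endpoint is an efficacy choice. Carrying it over to safety makes membership of the safety set depend on events after dosing. As written, three kinds of dosed patient would be missing from the proportions, if any exist:

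1. A patient who withdraws, at minimum one who withdraws consent.
2. A patient found ineligible after registration, although protocol 10.4.2 keeps such patients fully documented.
3. A patient who stops during cycle 1, if receiving at least one cycle is taken to mean completing it.

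The undefined term adds uncertainty. Patients stopped for toxicity most plausibly stay in the set. Protocol 10.4.1 continues their follow-up, 10.4.2 makes withdrawal of consent the only ground for exclusion from the study, and SAP 7.5(f) counts as treatment failure "discontinuation of therapy for any reason including death from any cause, progression, toxicity or add-on of new anti-cancer therapy". But one sentence in protocol 10.1 uses the word for an investigator's action: "Withdrawal in case the patients experiences an adverse event which indicates to the investigator that continued participation is not in the best interest". On that reading, the patients left out would be among those with the most relevant toxicity.

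Toxicity is a stated objective (SAP 2.1), and with 22 patients one or two exclusions move a proportion by a few percentage points.

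**Working it through.** **The plan's own figures.** Protocol 12.2 and 12.6.1 give 56 enrolled, 48 in the Core set, and a withdrawal rate below 15%.
- 48 × 1.15 = 55.2, rounded up to 56, which is the stated figure. Dividing instead, 48 / 0.85 = 56.47, gives 57.
- 1 − 48/56 = 14.3%, consistent with a rate below 15%.

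So up to 8 of 56 patients were expected to be outside the Core set, and therefore outside the safety set.

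**The trial as it stands.** SAP 2.1 gives 22 patients included. The eight who signed consent without meeting the criteria are additional to these, so no dosed ineligible patient is documented. The number of withdrawals is not given; SAP 7.3 only plans to tabulate it. At the planning ceiling, 0.15 × 22 = 3.3, or about 3.

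**Illustration.** Assumptions: all 22 were dosed, *w* are excluded, and 5 retained patients have an SAE. The plan reports 5/(22 − *w*) with a Clopper-Pearson 95% interval. The all-treated proportion runs from 5/22 (no excluded patient had an SAE) to (5 + *w*)/22 (all did).

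| *w* | Plan's proportion (95% CI) | All-treated range | All-treated minus plan (points) |
|---|---|---|---|
| 0 | 5/22 = 22.7% (7.8–45.4) | 22.7% | 0 |
| 1 | 5/21 = 23.8% (8.2–47.2) | 22.7% to 27.3% | −1.1 to +3.5 |
| 2 | 5/20 = 25.0% (8.7–49.1) | 22.7% to 31.8% | −2.3 to +6.8 |
| 3 | 5/19 = 26.3% (9.1–51.2) | 22.7% to 36.4% | −3.6 to +10.0 |

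Every all-treated value lies inside the plan's own interval.

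**Shorter observation.** An all-treated crude proportion has a small weakness of its own, because withdrawn patients are observed for less time. On schedule, cycle 18 day 1 is day 1 + 17 × 21 = 358, and the 110-day AE window (protocol 11.1.1) ends on day 468. Take *w* = 3, no data after withdrawal, full windows for the 19 retained patients, and the same constant risk for everyone. The risk by day *d* is 1 − (1 − 5/19)^(*d*/468), and the expected all-treated proportion is (5 + 3 × risk)/22.

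| Withdrawal day | Risk by that day | Expected all-treated proportion |
|---|---|---|
| 21 | 1.4% | 22.9% |
| 189 | 11.6% | 24.3% |
| 378 | 21.9% | 25.7% |

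Full observation would give 26.3%, so the all-treated proportion would be low by about 0.6 to 3.4 points. In this scenario, excluding withdrawn patients gives a slightly higher figure than including them. If withdrawn patients had more events, it gives a lower one.

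**The case against.** The strongest reply is that the exclusion was meant for the primary endpoint and is loosely placed. Protocol 12.6.1 does not contain it. Protocol 5.2 and 12.3 and SAP 5, 6 and 8.2.5 tie it to the confirmatory analysis. In SAP 4 it stands next to sentences about response and efficacy. SAP 7 applies descriptive methods to the whole study population. SAP 7.1 and 7.3 tabulate eligibility and withdrawal of consent, which would tell little in a set of eligible patients who did not withdraw. SAP 7.5 uses a withdrawn patient's data up to withdrawal. The safety analyses are descriptive, no decision rests on them, and in a trial this small the listings may let a reader recount. Finally, every count in the illustration is assumed, and retained patients may also stop early.

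Some of this stands. The intention may have been narrower than the text. Two of the three patient types are hypothetical, and no effect on a result has been shown. But the counter-text does not override an explicit rule. The phrase in SAP 7 is undefined and contrasts with the lymphoma subtypes. The provision in SAP 7.5 concerns the primary endpoint. The tables in SAP 7.1 and 7.3 only hint at wider outputs. Listings, even if complete, do not correct a reported proportion and its interval.

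**Conclusion.** The concern holds. Following SAP 4 to the letter removes withdrawn, treated patients from the headline safety proportions. Confidence is high that the rule does this and low that it changes a result in this trial, because the number of such patients is not given and may be zero.

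If one to three patients are affected, the SAE proportion could differ from the all-treated one by anything from −3.6 to +10.0 points under the assumed five retained patients with an SAE. The upper end requires three exclusions, all with an SAE. The direction is not known in advance. The event counts, exclusion counts, withdrawal days and constant risk are illustrative assumptions, as is the dosing of all 22. The point should be fixed, but it does not touch the primary test.

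**What to change.** - In SAP 4, define the safety population as all patients who received any amount of Rituximab or Pembrolizumab, regardless of eligibility, cycle completion or later withdrawal. Record this in SAP 3 as a change from protocol 12.6.2.
- Use this set for SAP 7.6, SAP 8.2.6 and the exposure outputs in SAP 7.7, with data up to withdrawal.
- Show each patient's days of AE observation beside the proportions, and state that crude proportions may be slightly low because withdrawn patients are observed for less time.
- Report the number of dosed patients outside the Core Analysis Population, with the reason for each.
- For the Core set, state whether withdrawal means withdrawal of consent only, and whether at least one cycle must be started or completed.

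The cost is one definition, one entry in SAP 3, the clarifying wording above and one column of observation days. Protocol 10.1 keeps data collected before withdrawal in the database, so nothing new has to be collected. If no patient is affected, the report will show that.
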